4.7.3 Concomitant therapy

All medications, including over the counter and herbal preparations, will be recorded from study enrollment until completion. Associated information will be recorded, including: reason for use, dosage (amount and frequency) and beginning/ending dates.

4.7.4 Background medication

Patients will be allowed to continue INCS spray prior to surgery. Following surgery all participants will undergo standardized postoperative treatment with continued INCS spray. This will be completed throughout the EOS visit.

Intranasal corticosteroid compliance will be recorded during study visits and compliance phone calls. If a subject cannot tolerate sinonasal irrigations, they should be screen failed prior to randomization.

4.7.5 Rescue therapy

During study treatment and off treatment follow-up, based on clinical evaluation, in case of worsening signs and/or symptoms consistent with an AECRS, the Investigator may consider rescue treatment. This typically involves corticosteroids or antibiotics delivered orally or topically to the sinonasal mucosa. Rescue therapies are not prescribed in this Protocol but will be recorded in the study database.

Patients receiving rescue treatment other than surgery during the study should continue on study drug unless the Investigator decides to withdraw the study treatment.

4.7.6 Treatment following study conclusion

Following the EOS visit, participants should resume standardized therapies [4] at the discretion of their healthcare team and local practice.

4.8 Pharmacy

Belmar Pharma Solutions (Lakewood, CO) will maintain and dispense study drug. [name] will be the lead pharmacist for this study. Once participants are randomized the pharmacy will be notified via REDCap. Study drug will be mailed directly to the subject in three-month intervals (Visits 3-6) during the course of the study and be sent on ice via overnight delivery with continuous temperature monitoring. The patient will bring their first dose with them to the clinic during Visit 3.

5. Procedures Involved

5.1 Nasal endoscopy

All study participants will undergo diagnostic nasal endoscopies at each study visit, per SoC, to monitor treatment outcomes[1]. Unique to this Protocol, a digital recording of the nasal endoscopy will be collected and stored centrally on a study approved repository. This will be completed in accordance with appropriate care for the management of CRSwNP.

5.2 Study Measures

The study design and endpoints will answer important clinical questions about the efficacy of dupilumab on mucosal inflammation and symptoms and effect on the number of rescue medications per subject after sinus surgery. Examining the effect of dupilumab after comprehensive sinus surgery for AFRS with clinically relevant endpoints addresses a clinical treatment pathway that has yet to be formally explored.

5.2.1 Objective measures of disease

Modified Lund-Kennedy Endoscopic Score:

Modified Lund-Kennedy score (mLK) is a validated measure of sinonasal inflammation, as evaluated by means of nasal endoscopy. The composite score ranges from 0 to 12, with increasing score representing worsening inflammation among three separate findings (Nasal polyps, Discharge, Edema). Each finding is rated from 0 (absent) to 2 (severe). $A \ge 2$ -point increase from baseline total postoperative score represents clinically significant worsening of sinonasal inflammation[5]. The treating physician will complete the nasal endoscopy per SoC,

with automated recording on local storage drives. Following completion of the patient encounter, study personnel will transfer this recording to the study database for central review and scoring. A blinded reader will review all nasal endoscopies to determine the mLK score.

Lund-MacKay Radiologic Score:

The change in radiographic opacification between baseline and EOT will be analyzed by the Lund- MacKay radiologic score (LM) [6]. The LM Radiologic scoring system assigns a value of 0, 1, or 2 to each of the following sinuses: maxillary, anterior ethmoid, posterior ethmoid, frontal, and sphenoid. Score assignments are 0 if the sinus is totally patent, 1 if the sinus is partially opacified, and 2 if the sinus is completely opacified. The osteomeatal complex is scored either 0 if not occluded or 2 if occluded. The maximum score for each side is thus 12, with a total score determined out of 24. Baseline LM scores will be assessed from baseline preoperative CT scan. Preoperative and EOT CT scans will be transferred to the study database by trained personnel, where the blinded reader may determine the associated LM score.

Endoscopic Nasal Polyp Score:

Endoscopic nasal polyp score is determined by the treating Investigator. Unlike prior study of dupilumab in nasal polyps, [7] we will separately record the Nasal Polyp Score for each side, with a maximum unilateral score of 4. This is appropriate for monitoring efficacy in AFRS, as a subgroup of participants may present with unilateral disease. This will be considered in statistical analysis and reporting of results (see Section 14.6- Primary Analysis).

Table 5: Endoscopic Nasal Polyp Score

Polyp Score	Polyp Size
0	No polyps
1	Small polyps in the middle meatus not reaching below the inferior border of
	the middle turbinate
2	Polyps reaching below the lower border of the middle turbinate
3	Large polyps reaching the lower border of the inferior turbinate or large
	polyps of score 2 with additional large polyps medial to the middle turbinate
4	Large polyps causing complete or near-complete obstruction of the inferior
	nasal cavity i.e. touching the floor of the nose

Spirometry:

Pulmonary function testing is performed according to the standardized methods of the lung function tests of the American Thoracic Society and European Respiratory Society. (Miller et al. 2005). The following parameters are measured or calculated: percent predicted vital capacity (%VC), forced vital capacity (FVC), forced expiratory volume in 1 second (FEV1), percent predicted FEV1 (%FEV1) and FEV1/FVC ratio.

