		7.2.1. Exclusion Criteria
		Removed mucocele as exclusion criteria as this frequently seen in
		AFRS.
3.7.2	9 Oct 2023	Schema
3.7.2	7 001 2023	Updated the schema to reflect the changes made to the protocol
272	2 App 2024	
3.7.3	2 Apr 2024	Across the protocol
		Asthma Control Test (ACT) was replaced by Asthma Control Questionnaire (ACQ) throughout the protocol.
		4.1 Overall Design Protocol election to allow appellment of participants within 2
		Protocol clarified to allow enrollment of participants within 2
		weeks of surgery if they have been on background therapy for a
		minimum of 2 weeks and meet all other eligibility criteria.

Protocol Title: S-I: Add-on Dupilumab for AFRS as Postoperative Therapy (ADAPT)

Table of Contents

1.	Study Summary	8
2.	Background	
3.	Study Objectives and Endpoints	
4.	Study Intervention/Investigational Agent	
5.	Procedures Involved	22
6.	Data Specimen Banking	24
7.	Inclusion and Exclusion Criteria	24
8.	Local Number of Participants	27
9.	Recruitment Methods	28
10.	Withdrawal of Participants	28
	Risk to Participants	
12.	Potential Benefits to Participants	28
13.	Compensation to Participants	29
	Data Management and Confidentiality	
15.	Provisions to Monitor the Data to Ensure the Safety of Participants	33
	Provisions to Protect the Privacy Interest of Participants	
17.	Informed Consent	40
18.	Setting	40
19.	Appendix	41
20.	Resources Available	58
21.	Multi-Site Research monitoring	58
22	References	50

1. Study Summary

Table 1: Schedule of Activities

	Run-	Surgery Randomized Treatment period						EOT	EOS			
	in											
Visita	1	2	3		4		5		6		7	8
Week	W-6	W-1	W0	2,4,6,8,10 ^b	12	14,16,18,20,22 ^b	24	26,28,30,32, 34 ^b	36	38,40,42,44,46,48, 50 ^b	52	64
Day ± 7	D-42	D-7g	D0		D84		D168		D252	_	D364	D448
Informed consent	X											
Inclusion and exclusion criteria	X		X									
Patient Demography	X											
Medical / surgery history	X											
Physical exam	X		X		X		X		X		X	X
Urine Pregnancy Test ^c	X		X		X		X		X		X	X
Transfer diagnostic nasal endoscopy to online repository	X		X		X		X		X		X	X

D	37		37		37		37		37		37	37
Determination of			X		X		X		X		X	X
mLK endoscopic												
score ^d												
Spirometry ^e	X		X		X		X		X		X	X
SNOT-22	X		X		X		X		X		X	X
ACQ	X		X		X		X		X		X	X
CT sinus scan	X^{i}										X	
Randomization		X										
Collect	X		X		X		X				X	X
peripheral												
bloodh												
Sinus mucus	X		X		X		X				X	X
sampleh	1											
Ethmoid sinus		X										
tissue												

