4.1 Overall Design

This is a multi-center, randomized, double-blinded, placebo-controlled, parallel group study to evaluate the efficacy of dupilumab 300mg administered subcutaneously (SC) every 2 weeks versus placebo in participants with AFRS following planned sinus surgery.

132 participants will be randomized to receive dupilumab 300mg SC or matching placebo while on a background of intranasal corticosteroid sprays twice daily. Patients will be stratified by study site and by baseline comorbid asthma status (yes vs no). ~25% of the randomized participants will have comorbid asthma.

Eligible participants will enter a screening/run-in period on twice daily nasal saline irrigations followed by INCS spray for 2-6 weeks prior to planned sinus surgery. Participants may be consented and enrolled at any time during this 2-6 week run-in period, provided the failure of appropriate medical therapy has been documented as outlined in the inclusion criteria. Eligible participants already on study background therapy for at least two weeks may be consented and enrolled during the pre-surgery period.

Both saline irrigations/INCS and sinus surgery will be completed per standard of care (SoC) and not according to the study protocol. Patients who continue to meet eligibility criteria following surgery will be randomized 1:1 before Visit 3 (Day 0) when they receive placebo or dupilumab 300mg SC every 2 weeks. Patients will receive a total of 26 doses of IMP, via either study

personnel (Visit 3-6 at W0, 12, 24 and 36) or home-administration (W2, 4, 6, 8, 10, 14, 16, 18, 20, 22, 26, 28, 30, 32, 34, 38, 40, 42, 44, 46, 48, 50) to maintain a 2-week treatment schedule. Patient compliance will be recorded via text messages the day of scheduled home administration, as well as monthly phone calls and collection of used syringes during scheduled study visits (Visit 4-7 at W12, 24, 36 and 52). An EOT visit will be conducted at Week 52 (Visit 7). Patients will then be monitored on daily saline irrigation and INCS spray for 12-weeks to evaluate potential disease recurrence after discontinuation of IMP. An EOS visit will be conducted at Week 64 (Visit 8).

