14.1 Sample Size and Power analysis

A sample size of 66 participants per group achieves 90% power to detect a mean difference of 2 points on the modified Lund-Kennedy Endoscopic score at 52 weeks with a standard deviation of 3.5 and significance level of 0.05 using a two-tailed test. The clinically meaningful mean difference of 2 points and the standard deviation are based on previous study of mLK in a heterogeneous population with nasal polyps [5].

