14.6 Primary Analysis

To examine changes in the co-primary outcomes, the modified Lund-Kennedy score and the incidence of oral corticosteroid utilization per participant, a mixed effects longitudinal model will be fit that includes group (dupilumab, placebo) as a between participants factor and time (randomization through post-treatment period) as a categorical within participants factor plus their interaction term. Time is treated as categorical so that we can use the group-time interactions with the time main effect to estimate and test intent-to-treat (ITT) group differences at each time point, with 52 weeks as our primary ITT test. As randomization is stratified by site, site will also be included in the model. This mixed effects model allows incorporation of a random intercept term for each subject, different numbers of measurements (in case a visit is skipped), and the choice of appropriate variance-covariance structure. The mixed model will also permit identification of any significant changes in the post-treatment period from 52 to 64 weeks. This primary mixed model will incorporate all subject's randomized.

The primary objective will be assessed by testing this null hypothesis: treatment with Dupilumab post-surgery is equivalent to treatment with placebo post-surgery at 52-week end of treatment. The additional time point at 64 weeks is included in the model to ensure efficient evaluation of both co-primary outcomes at the EOT and 12 weeks after EOT. Significant changes between weeks 52 and 64 will be examined by linear contrast. We will test the following null hypotheses against two-sided alternatives:

- H₀₁: there is a lack of difference between the changes in mLK from baseline to 52 weeks and from baseline to 64 weeks for the untreated.
- H_{02} : there is a lack of difference between the changes in mLK from baseline to 52 weeks and from baseline to 64 weeks for the treated.
- H_{03} : the treatment effect dissipates between 52 and 64 weeks.

The primary estimand for the primary endpoint is the composite/treatment policy strategy. The intercurrent events will be handled as follows:

- Undergoing sinus surgery for AFRS: data after surgery will be assigned the worst possible score (composite strategy)
- Taking SCS or other rescue medications: data collected after use will be used in the analysis (treatment policy strategy)

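### The primary mLK model prespecifies no pre-operative severity covariate, although one is on hand for every participant; the open confounder clause in 14.7 should be replaced by a named covariate

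*Combined protocol and SAP*

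**What the plan says.** **Model.** Section 14.6 gives the primary mixed model as group, categorical time running from randomisation to the post-treatment period, their interaction, and a random intercept per participant. The one further term it names is site: "As randomization is stratified by site, site will also be included in the model". The primary test is the group difference at Week 52.

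**Covariate clause.** The last sentence of section 14.7 allows the primary and secondary models to take in potential confounders that are significant. It lists none and gives no selection rule. Section 14.5 also plans two-sample tests of baseline balance.

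**Pre-operative data.** Section 7.1.3 sets minimum SNOT-22 and CT Lund-MacKay scores for enrolment, so both are known for every participant before randomisation. On the CT score, section 5.2.1 says: "Baseline LM scores will be assessed from baseline preoperative CT scan". A footnote to Table 1 accepts a scan from the previous 6 months. Table 1 also has a row "Transfer diagnostic nasal endoscopy to online repository", marked at Visit 1.

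**Scoring.** Section 5.2.1: "A blinded reader will review all nasal endoscopies to determine the mLK score". In Table 1 the mLK determination row seems to be first marked at Visit 3 (Week 0), after surgery.

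**Power.** Section 14.1: "A sample size of 66 participants per group achieves 90% power to detect a mean difference of 2 points", with a "standard deviation of 3.5 and significance level of 0.05 using a two-tailed test". These planning values are "based on previous study of mLK in a heterogeneous population with nasal polyps".

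**The concern.** Every participant has comprehensive sinus surgery before randomisation, so the Week 0 mLK is a post-operative reading. It is not the same variable as the severity of disease that led to surgery. If pre-operative severity predicts who relapses by Week 52, a model without it gives a wider confidence interval for the mLK difference than the collected data allow. Chance imbalance in severity between arms of 66 would then be dealt with only if someone chose to add a covariate later.

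The covariate clause in 14.7 raises a separate matter that does not depend on any correlation. Letting significance decide what enters the primary model means that the primary estimate depends on choices made after the data are seen. The protocol already regards disease severity as a relevant covariate in 14.6, but only in a conditional Cox model for the unilateral subgroup.

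**Working it through.** **1. Inputs.** From section 14.1: 66 per arm, difference 2 points, SD 3.5, two-sided 0.05, stated power 90%. The total of 132 is in section 4.1. The within-arm correlation r between pre-operative severity and Week 52 mLK, beyond what the rest of the model explains, is not in the documents. It is an assumption, shown from 0.1 to 0.5.

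**2. The plan's own figure.** The standard error is 3.5 × √(2/66) = 0.609, and the noncentrality is 2/0.609 = 3.28. With 130 degrees of freedom the noncentral t gives power 90.3%, and 66 is the smallest number per arm that reaches 90%. The normal approximation gives 90.7%. The stated 90% is reproduced.

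**3. With a covariate.** Replace the SD by 3.5 × √(1 − r²). The variance falls by the fraction r², which is worth 1/(1 − r²) − 1 in extra participants. The 0.025 column assumes that the Bonferroni correction in 14.6 is split over the two co-primary endpoints; the plan does not state the number of tests.

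| r | Residual SD | Power at 0.05 | Power at 0.025 | Equivalent extra participants |
|---|---|---|---|---|
| 0 | 3.50 | 90.3% | 84.4% | 0 |
| 0.1 | 3.48 | 90.6% | 84.75% | 1% |
| 0.2 | 3.43 | 91.4% | 85.9% | 4% |
| 0.3 | 3.34 | 92.7% | 87.8% | 10% |
| 0.4 | 3.21 | 94.5% | 90.4% | 19% |
| 0.5 | 3.03 | 96.4% | 93.5% | 33% |

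These figures are for the group difference in the Week 52 score itself.

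**4. The contrast matters.** Section 3.1 defines the endpoint as change from baseline, while 14.6 tests group differences at each time point. A simulation compared the two (66 per arm, six visits, residual within-participant correlation 0.3, covariate unrelated to the Week 0 score). Variance of the estimated group difference:

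| r | Contrast | No covariate | Main effect only | With covariate-by-time term |
|---|---|---|---|---|
| 0.3 | Week 52 score | 0.380 | 0.346 | 0.346 |
| 0.3 | Change from Week 0 | 0.526 | 0.526 | 0.494 |
| 0.5 | Week 52 score | 0.370 | 0.282 | 0.282 |
| 0.5 | Change from Week 0 | 0.560 | 0.560 | 0.469 |

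On the change scale a main effect alone gains nothing, because it cancels in the difference between two visits. With the interaction at r = 0.5 the variance falls by 1 − 0.469/0.560 = 16%, against about 24% for the Week 52 score. In participants that is about 19–20% rather than 33%.

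**5. Scoring at Visit 1.** Read as written, 5.2.1 covers the Visit 1 recording; Table 1, if its mLK row is blank there, does not. The extracted text of Table 1 is damaged at this row: a line of unexplained marks, one of them under Visit 1, sits directly above the mLK label. The original table has to be checked before the two places are called contradictory.

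**The case against.** The strongest reply is that this is an optional gain of unknown size, partly provided for already.

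- **The plan leaves room for covariates.** Section 14.7 does, so it would be wrong to say that severity can never enter the model. That stands. What remains is that no covariate is named and that significance decides.
- **Nothing in the documents shows that pre-operative CT or endoscopy score predicts Week 52 mLK.** The predictor of poor surgical outcome named in the Background is mucosal eosinophil infiltration. Complete surgery may weaken any link, and Week 0 mLK is already in the model as a time point, so only information beyond it counts. This stands, and it is why only a range can be given.
- **The covariates are imperfect.** The CT may be up to 6 months old, and Visit 1 may fall anywhere in the run-in or pre-surgical period. Both could lower r.
- **Several covariates, each crossed with time, would be costly.** This stands too; the evidence supports one.

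A reader might infer that the Visit 1 endoscopies will go unscored and their information be lost. The documents do not support that: 5.2.1 says that all endoscopies are reviewed, the recordings are kept, and the Table 1 row is unclear. A reader might also infer that a gain worth a third more participants is being given up. That needs r = 0.5 and the Week 52 score contrast.

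**Conclusion.** The point holds as a prespecification gap with a possible gain in precision. The primary mLK model names no pre-operative severity measure, one is available for every participant before randomisation, and the only route for it in the plan is selection by significance. Fixing the covariate in advance is better than that route whatever r turns out to be.

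The gain in power is conditional. At two-sided 0.05 it is about 1 percentage point at r = 0.2, about 2.4 at r = 0.3 and about 6 at r = 0.5, for the Week 52 score contrast; it is smaller for change from baseline. At 0.025, on the assumption of two tests, r of about 0.4 would bring power from 84.4% back to about 90%.

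It would go too far to read this as bias or as a faulty sample size. Omitting a prognostic covariate from a randomised comparison of means does not bias it, and the stated 90% at 0.05 is reproduced without any covariate.

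**What to change.** Before unblinding:

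1. In 14.6, name one pre-operative severity covariate for the primary mLK model: pre-operative Lund-MacKay, or Visit 1 mLK from the blinded reader. Enter it with a covariate-by-time interaction and keep it whatever its significance. State that this replaces the open clause in 14.7 for that model.
2. If Lund-MacKay is chosen, say whose reading is used, since 5.2.1 says only that the blinded reader may score it.
3. Check the original Table 1. If the mLK row is blank at Visit 1, reconcile it with 5.2.1 so that the Visit 1 recording is scored.

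Cost: SAP wording; one covariate over six time points (Weeks 0, 12, 24, 36, 52 and 64), so six parameters; and, if Visit 1 mLK is used, up to 132 readings by the existing reader, which 5.2.1 already promises. No new visit or procedure is needed, and the sample size need not change.

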Treatment:										. 		
IMP:			X	X	X	X	X	X	X	X		
Dupilumab/												
placebo												
injection ^b												
Record	X	X	X		X		X		X		X	X
concomitant												
medications												
Text reminder				X, X, X, X,		X, X, X, X, X		X, X, X, X,		X, X, X, X, X, X,		
for IMP self-				X		11, 11, 11, 11, 11		X		X		
administration ^b				11						11		
Assessment				X, X		X, X		X, X		X, X, X		
of IMP				21, 21		71, 71		71, 71		71, 71, 71		
compliance												
(phone												
call) ^b												
Caii)												

Assessment of IMP			X	X	X	X	
compliance							
(device							
collection)b							
Record planned							
surgery for NP,							
OCS use and		 	 	 X	 	 	
other rescue							
medications							

^a Patients who discontinue treatment early will be assessed as soon as possible using the procedures normally planned for the EOT Visit.

ACQ: Asthma Control Questionnaire, AE: Adverse Event, CT: Computed Tomography, IMP: Investigational Medical Product, mLK: Modified Lund Kennedy Endoscopic Score, NP: Nasal Polyp, OCS: Oral Corticosteroid, SAE: Serious Adverse Event, SNOT-22: 22-item SinoNasal Outcomes Test, WOCBP: women of childbearing potential

^b Patients will self-administer investigational drugs between study visits (v3-8). Compliance will be ensured by reminder text messages the day of each home injection, monthly phone calls and collection of injection materials at following study visits.

^c Urine pregnancy test completed by all WOCBP, (i.e., post-pubescent, premenopausal females).

^d Determination of mLK endoscopic scores will be completed by a blinded, central reader for all study sites.

^e Lower airway assessments completed for participants with medical history of comorbid asthma (~25% of study cohort).

^f Patients will be randomized once pathology report is available post-operatively to confirm presence of fungus.

^g Surgery period can be extended to 4 weeks to accommodate operating room availability, unforeseen personal events, or other occurrences that delay randomization.

^h Optional, only in participants that consent to collection and banking of these materials.

ⁱ If not previously obtained within prior 6 months.

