3.2 Secondary Objectives

Secondary objectives	Endpoint/variable(s)	
	Change from baseline at 52 weeks both within	
	and between treatment and placebo arms	
To evaluate the effect of dupilumab on:		
Prevention of revision surgery for AFRS	Prevalence of revision sinus surgery for recurrent nasal polyps, and comparison of survival curves	
Secondary objective measures of sinonasal	• Endoscopic nasal polyp score (NPS)	
inflammation following sinus surgery	CT generated Lund-MacKay score	
• Lower airway dysfunction following sinus surgery in the subgroup of participants with asthma (~25%)	Spirometry	
• Upper and lower airway, disease-specific,	• 22-item sinonasal outcomes test (SNOT-22)	
health-related quality of life	Asthma Control Questionnaire (ACQ)	
Reducing utilization of rescue medications for acute exacerbations of CRS following sinus surgery	 Prevalence of oral / topical corticosteroid utilization per treatment cohort Incidence of oral / topical antibiotic utilization per subject Prevalence of oral / topical antibiotic utilization per treatment cohort 	

Other secondary objectives	Endpoint/variable(s)
	Change from end of treatment (EOT) to end of

	study (EOS)
To evaluate the effect of dupilumab on:	
Objective measures of sinonasal	Endoscopic modified Lund-Kennedy
inflammation following sinus	(mLK) score
surgery	• Endoscopic nasal polyp score (NPS)
• Upper and lower airway, disease-specific,	• 22-item sinonasal outcomes test (SNOT-22)
health-related quality of life	Asthma Control Questionnaire (ACQ)

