14.7 Secondary and Exploratory analyses

In a secondary analysis, a similar mixed model as described above will be fit that includes the subset of participants who are receiving treatment (dupilumab or placebo) for both nostrils. This model will incorporate nesting factors to identify repeated measures by subject and by nostril.

In an exploratory analysis, we will also compare the proportion of participants whose modified Lund- Kennedy score improved by greater than or equal to 2 units. For participants who undergo sinus surgery for AFRS prior to Week 52, non-responder imputation will be used. We will utilize a Chi-square or Fisher's exact test to examine if this proportion is significantly different by treatment group (dupilumab or placebo) at 52 weeks.

For the continuous secondary outcomes (e.g. SNOT-22 score, NPS, FEV1), a mixed effects longitudinal model will be fit that includes group (dupilumab, placebo), time (randomization through post-treatment period), and their interaction term in a similar fashioned as described for the primary outcome modified Lund-Kennedy score. For the secondary outcomes that compare the number of participants requiring rescue treatment and the number of adverse events (safety) over 52 weeks, similar mixed effects models will be fit but with consideration of a Poisson distribution (as opposed to normal distribution). The mixed effects models for both primary and secondary outcomes will permit the inclusion of any significant potential confounders.

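### Lund-Mackay change is measured from a preoperative CT, so within-arm change cannot be read as a dupilumab effect, and the form of the between-arm analysis is not pinned down

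*Combined protocol and SAP*

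**What the plan says.** Section 3.2 lists "CT generated Lund-MacKay score" among the secondary endpoints, under an introduction about the effect of dupilumab and a column heading that reads "Change from baseline at 52 weeks both within" and continues "and between treatment and placebo arms".

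Section 5.2.1 says "The change in radiographic opacification between baseline and EOT will be analyzed by the Lund- MacKay radiologic score (LM"), with "The maximum score for each side is thus 12, with a total score determined out of 24", and then: "Baseline LM scores will be assessed from baseline preoperative CT scan". Table 1 schedules sinus CT at Visit 1 and at Week 52 only. The footnote to the Visit 1 scan reads "If not previously obtained within prior 6 months", so an existing scan up to six months old may serve. Section 7.1.4 requires comprehensive surgery before randomisation. No scan lies between surgery and first dose.

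For the continuous secondary outcomes, section 14.7 prescribes a mixed model with group, time and their interaction, built like the primary model. Its time factor is "time (randomization through post-treatment period"). Lund-Mackay is not among the examples named there, but no other analysis of a continuous secondary outcome is offered. The model in 14.6 that it follows tests group differences at each time point. Section 14.7 allows significant confounders to be added; it does not name the preoperative Lund-Mackay score as a covariate.

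**The concern.** The secondary objective is sinonasal inflammation after surgery, but the Lund-Mackay baseline precedes surgery. The mLK score is first determined at Week 0 in Table 1, and 5.2.1 judges its worsening from a postoperative baseline. The phrase change from baseline therefore means two different things for two sinus endpoints.

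Two consequences follow. First, a fall in Lund-Mackay within the dupilumab arm would contain the whole effect of the operation, yet 3.2 lists it as evidence on the drug. Second, the between-arm analysis can be read in two ways, as a comparison of changes or of Week 52 scores. The two have different precision, neither is the most precise use of the two scans, and the choice could be made after the data are seen. This is the trial's only imaging endpoint.

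**Working it through.** **The plan's own figure.** The only power statement is for mLK (14.1): difference 2, SD 3.5, two-sided 0.05, 66 per group. The normal approximation gives n = 2 × (1.960 + 1.282)² × 3.5² / 2² = 64.4, so 65 per arm for 90% power; 66 per arm gives 90.7%. The figure reproduces. There is no corresponding figure for Lund-Mackay, and 14.10 says the study is not designed to detect differences in secondary outcomes.

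**Inputs assumed.** The documents give no Lund-Mackay SD, no effect size and no correlation between the preoperative and Week 52 scores. Write s0 and s1 for the preoperative and Week 52 SDs and r for the correlation. The range examined is r from 0 to 0.7 and s0/s1 from 0.75 to 1.25.

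**Within-arm change.** Take SD 5 at both times (assumed), no drug effect and 66 placebo participants. The SE of the mean change is 5 × √(2(1 − r)) / √66.
- Net fall of 4 points at r = 0: SE 0.870, 4/0.870 − 1.96 = 2.64, so the change is significant with probability 99.6%; higher at larger r.
- Net fall of 2 points: 63% at r = 0, 90% at r = 0.5.

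A significant within-arm fall therefore needs no drug effect.

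**Between-arm bias.** Both arms are operated on before 1:1 randomisation, so the surgical effect cancels. Simulating 4,000 trials with an assumed 8-point placebo fall and a true drug effect of −2, the mean estimate was between −1.97 and −2.00 for the change score, the Week 52 score alone and ANCOVA.

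**Between-arm precision.** Per-participant variances in large samples:
- change score: s0² + s1² − 2·r·s0·s1
- Week 52 score alone: s1²
- Week 52 score adjusted for the preoperative score (ANCOVA): s1²(1 − r²)

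The change score exceeds ANCOVA by (s0 − r·s1)², and the Week 52 score alone exceeds it by r²·s1². Neither excess can be negative. With s0 = s1 the SE ratios to ANCOVA are √(2/(1 + r)) and 1/√(1 − r²):

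| r | Change score: SE excess | 66 per arm is worth, under ANCOVA | Week 52 alone: SE excess |
|---|---|---|---|
| 0 | 41% | 33 | 0% |
| 0.2 | 29% | 40 | 2% |
| 0.4 | 20% | 46 | 9% |
| 0.7 | 8% | 56 | 40% |

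With unequal SDs the change-score loss moves either way. At s0/s1 = 1.25 and r = 0.5 the variance ratio to ANCOVA is 1.3125/0.75 = 1.75. At s0/s1 = 0.75 and r = 0.7 it is 0.5125/0.51 = 1.00, so the loss disappears. The change score is less precise than the Week 52 score alone only when r < s0/(2·s1), which is 0.5 with equal SDs.

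**Which contrast the plan would report.** If the preoperative scan were put into the 14.7 model as a first time point, the group-by-time term would equal the difference in changes, and group plus interaction would equal the Week 52 difference. A trial fit confirmed both (−0.724 and −1.232 in one simulated data set). As 14.7 is written, the preoperative scan falls outside the time range, leaving one Lund-Mackay value per participant and no change to estimate.

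**The case against.** The strongest reply is that the comparison that matters is randomised. A reader might infer from the preoperative baseline that the endpoint mainly measures the operation. That is not so between arms, where surgery cancels and the estimate is unbiased.

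A reader might also infer that both arms are bound to show apparent benefit. The documents do not support that. They give no Lund-Mackay values, and section 2 expects polyps to recur aggressively, often within months of surgery, so the placebo arm may have lost part of its fall by Week 52. Apparent benefit in both arms is likely, not certain.

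Nor can the 41%, 29% and 20% figures be taken as the plan's loss. They apply to a change-score test with equal SDs and low r. Sections 14.6 and 14.7 can equally be read as testing the Week 52 difference, which at the same r loses 0%, 2% and 9%. Nothing in the documents shows that r is low.

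It can further be said that 3.2 sets within-arm beside between-arm comparison, that 5.2.1 is open about the baseline being preoperative, and that the endpoint is unpowered. All of this stands and limits the weight of the point. It does not make the within-arm change interpretable as a drug effect, nor say which between-arm contrast will be reported.

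**Conclusion.** The point holds in limited form. Within-arm Lund-Mackay change combines surgery, relapse and treatment and is not evidence on dupilumab; this follows from the schedule alone and needs no assumption. The between-arm comparison is unbiased but inconsistently specified between 5.2.1 and 14.7, and adjustment for the preoperative score is not prespecified.

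The size of the precision loss is conditional, because it rests on an assumed r and assumed SDs. With equal SDs it runs from 41% down to 8% in SE for a change score, and from 0% up to 40% for an unadjusted Week 52 score, as r goes from 0 to 0.7. It can vanish for the change score when the preoperative SD is the smaller one and r is high. Without knowing r, ANCOVA is the safe choice: in large samples it is at least as precise as either alternative.

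Lund-Mackay is an unpowered secondary endpoint. The total of 132 participants and the co-primary conclusions do not change.

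**What to change.** - In 14.7, name the Lund-Mackay analysis: the Week 52 score compared between arms by ANCOVA, with preoperative Lund-Mackay and site as covariates, in place of the longitudinal model. Add asthma status once the sections are reconciled on whether it is a stratum: 4.1 lists site and asthma, 4.7 and 14.4 list site only.
- Keep the plan's handling of missing data (14.8) and of repeat sinus surgery (14.6), and say so for this endpoint, since 14.6 words its surgery rule for the primary endpoint.
- In 3.2 and 5.2.1, report within-arm Lund-Mackay change descriptively only, labelled as change from before surgery and including the effect of surgery.

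The cost is SAP wording. Both scans are already scheduled, and 7.1.3 already requires a Lund-Mackay score at enrolment. No procedure or participant is added. The only statistical cost is estimating one more coefficient, which is negligible at 66 per arm: in the simulation at r = 0, the worst case for adjustment, the SE was 0.881 against 0.876 for the Week 52 score alone.
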